Wear Experience with Daily Disposable Contact Lenses over a Long Day

NCT04535310

Version dated 14Oct2020

Wear Experience with Daily Disposable Contact Lenses over a Long Day

[name], OD MS

The Ohio State University College of Optometry
Innovation in Vision and Eye care Research Group - iVERG
[name]
[name]
[contact]

Purpose

The purpose of this study is to explore the performance of PRECISION1® lenses on long days of lens wear.

Study Overview

This open-label study is of current soft contact lens who wear contact lenses for longer than a typical work day. Participants will be fit into PRECISION1® contact lenses, or may be existing PRECISION1® contact lens wearers. Participants will be assessed after 1-2 weeks of wear with a follow up visit to insure a successful lens fit. Subject will then be sent links to a survey to complete immediately about their current comfort and vision with lens wear and their status with digital device use at 10, 12, 14 and 16 hours of lens wear each night for 1 week. Participants will return for a final follow-up visit including a VAS survey and the CLDEQ8 survey of their lens wear experience.

Background

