Soft daily wear contact lenses are used by an estimated 40.9 million adults in the United States.¹ Contact lenses which are worn for daily wear are considered minimal risk by the FDA, and risks to wearers are minimized by proper lens care and hygiene. Daily disposable contact lenses do not require daily cleaning and overnight storage, which improves the required amount of time to care for contact lenses. In addition, daily disposable contact lenses are associated with less lens deposits, which decreases associated comfort issues in lens wearers, including decreasing the risk of triggering Giant papillary conjunctivitis (GPC) and/or ocular allergic responses in patients.² Additionally, daily disposable contact lens wearers are not likely to expose their lenses to water and tend to have better lens hygiene since these lenses do not require daily cleaning. This is reflected in a study which found less superficial punctate staining and symptoms of dryness when comparing daily disposable contact lens wear with planned replacement lenses.³ The subjects in this study will be fit into PRECISION1 daily disposable contact lenses, which are less likely to be associated with the already minimal risks of daily contact lens wear. Because of these benefits of daily disposable lenses, and the accompanying improvement in comfort, it is likely that these lenses will provide long lasting comfort and vision throughout the day. As many people wish to wear their contact lenses to work and then throughout the evening, it is of interest to know how a lens performs over the course of a day into evening.

Key Endpoints:

- Subjective assessment of comfort and vision at time points of extended contact lens wear.
- Visual Analog Scale survey of lens wear symptoms (comfort, dryness, vision)

Study Time Points:

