Visit 1 will be conducted to consent the subject and determine eligibility. Consenting will be conducted via phone call and REDCap and will occur before the subject arrives on site if possible. After consenting, the visit will begin with visual acuity and an evaluation of the subject's ocular health will occur to determine eligibility including positively responding to the question, "Do you currently wear contact lenses over a long day?" This will ensure that subjects are able and willing to participate in the study since long contact lens wear will be needed. Subjects will be asked their normal morning time for inserting lenses and evening time for lens removal. Eligible subjects can be habitual wearers of PRECISION1® Contact Lenses or will be fit into PRECISION1® Contact Lenses. Participants will be fit with PRECISION1® Contact Lenses at this visit and will have a fit assessment and over-refraction completed in order to obtain the best fit and vision. Upon successful fit of lenses, subjects will complete an initial survey of lens experience. Lenses will be dispensed to eligible participants and a second visit will be scheduled.

Visit 2: Precision 1 follow-up visit will occur approximately 1 week (± 3 days) following Visit 1. Visual acuity and contact lenses fit assessment and over-refraction will be completed. If changes to the lens are necessary, those changes will be made and an additional follow up visit will be scheduled. Subjects will be asked their normal morning time for inserting lenses and evening time for lens removal. Subjects who are new to PRECISION1® Contact Lenses will be dispensed additional lenses to wear until Visit 3.

Five evening survey days: On the morning of each survey study day, the subject will report their time of lens insertion to study staff or by entering the time in a RedCap survey. Study staff will communicate with participants by sending a link to complete a brief survey at 10, 12, 14 and 16 hours of lens wear that day via REDCap. The surveys will be deployed on 5 days between Visit 2 and Visit 3 that are determined at the time of Visit 2. Every attempt will be made to complete the surveys on business days if possible.

Final visit: The contact lens follow up visit will occur approximately 1 week (± 3 days) following the follow up visit. Subjects will have visual acuity, an assessment of ocular health. Subjects will then complete surveys about their lens wear experience.

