Evening Surveys will include 1-10 forced choice grading of comfort and vision.

End of study surveys will include VAS scales assessing:

- Overall Quality of vision
- End of Day Quality of vision
- Overall comfort

End of Day comfort
Overall dryness
End of Day dryness

Recruitment

Potential subjects may see posters placed on bulletin boards at The Ohio State University or local eye care offices, emails to students, faculty and staff at OSU, online or paper ads, or signs on the OSU buses. A search of the electronic medical records of The Ohio State College of Optometry may be done to identify possible subjects who then may be contacted by email or phone with information about the study. Word of mouth referrals by study team members to OSU employees and friends may occur. Emails to alumni of the OSU College of Optometry may be sent for local doctors to notify eligible potential subjects about the study.

Inclusion criteria:

- Ages 18-40
- Subjects must be current spherical contact lens wearers with longs days of lens wear
- Subjects must have 20/25 or better distance visual acuity with current lenses.
- Subjects should have had an eye exam in the past year (self report).
- Good general health (defined by medication use that has not changed within the last month and the absence of medical conditions or treatments that are deemed confounding to the data as determined by the PI).
- Ability to give informed consent.
- Subjects must have a working smart phone and be willing to download an app and/or receive and respond to texts and emails.
- Willing to spend time for the study. Subjects will be required to attend three study visits, wear contact lenses on days between study visits, and must respond to communications on a smart phone on 5 days between visits 2 and 3.
- Either gender.
- Any racial or ethnic origin.

Exclusion criteria:

- No current ocular inflammation or infection as assessed by the study investigator.

Consent and Confidentiality

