A team member trained in the consent process will provide the consent document for the potential subject to read and will review the procedures with reference to the consent form. The individual is then provided with time to read the consent form and offered the opportunity to ask questions. The participant is explicitly told that they may stop participation at any time. All subjects will have the capacity to give informed consent. If there is any doubt as to the subject's ability to consent to the study, the subject will be excluded from the study. If the subject agrees to take part in the screening or measurement, he or she will sign and date the most recent IRB-stamped consent as will the team member. The subject will be provided with a copy of the consent form.

The investigator team is trained in privacy issues and will be reminded of the importance of patient privacy prior to study initiation. Potential study participants will contact us after seeing advertisements, emails or hearing about the study by word of mouth, giving them the choice of whether or not they wish to participate in a study for people with dry eyes. Privacy is protected by limiting information related to study recruitment only, and no other personal or medical information that should be private to the patients. The PHI needed is only for the purposes of this study. It is highly unlikely, indeed extremely remote that the dry eye symptoms or signs are related to private or personal information that should or would be preferred to be kept confidential to the patients. Risk factors for dry eye rarely relate to matters or conditions that would be personal to the patient such as personal relationships, behaviors or diseases that one prefers to keep private and confidential.

Statistical Analysis and Power Calculation

This small sample size was chosen for convenience as this study as enrollment for evening participation may be difficult.

Statistical analysis will include descriptive statistics.

Data Management and Security

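### Team members may refer friends and OSU employees into an open-label, single-lens study with self-rated key endpoints, and the plan neither excludes close contacts nor provides for identifying them

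*Combined protocol and SAP*

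**What the plan says.** Among several recruitment routes (posters, emails, advertisements, bus signs, a record search, emails to alumni), the Recruitment section includes this one: "Word of mouth referrals by study team members to OSU employees and friends may occur". The Consent and Confidentiality section mentions the same route: "Potential study participants will contact us after seeing advertisements, emails or hearing about the study by word of mouth".

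The Study Overview describes an open-label study, and only one named lens is worn. The first key endpoint is "Subjective assessment of comfort and vision at time points of extended contact lens wear"; the second is a visual analogue scale (VAS) survey of comfort, dryness and vision. On the instrument for the first, the plan says: "Evening Surveys will include 1-10 forced choice grading of comfort and vision".

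The single exclusion criterion concerns ocular inflammation or infection. The investigator's discretion under the general-health inclusion criterion extends only to medical conditions and treatments. The Statistical Analysis and Power Calculation section gives no sample size, calls the sample small and chosen for convenience, expects that enrolment may be difficult, and plans descriptive statistics only.

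**The concern.** A subject who knows a team member personally has a reason to rate the lens kindly that a stranger does not have. The Background section states the expected answer, namely that the lens is likely to stay comfortable and give good vision through the day, and people close to the team are the subjects most likely to know it. The right name for this is courtesy or social-desirability bias. Acquiescence bias concerns agree/disagree items, and these are numeric and VAS ratings.

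In a randomised comparison, a favourable tendency shared by both arms would largely cancel. Here there is one arm, and the levels of the ratings are what the key endpoints describe, so any such tendency would go straight into them. If nobody notes who the associates are, neither the study team nor a reader can judge afterwards how far the levels depend on them.

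**Working it through.** The plan states no figure on this point, so there is none to reproduce. The check is a reading of the text, followed by an illustration of scale.

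**1. Is the route open?** Yes. The Recruitment section permits it in terms.

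**2. Does any eligibility rule close it?** No. The one exclusion criterion is ocular, and the investigator's discretion is medical. Neither reaches a relationship with the team.

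**3. Does any section provide for identifying such subjects?** None does. The Visit 1 description lists consent, acuity, ocular health, the long-day question, usual insertion and removal times, fit, over-refraction and an initial survey. The Data Management and Security section describes a file of potential subjects and a file of enrolled subjects with contact information, but mentions no field for route or relationship. It also has electronic files containing protected health information destroyed at the end of the study. The paper consents are kept, but nothing in the plan suggests that they would show the relationship.

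**4. Are the ratings kept from the team?** No section says so. Questionnaires are held in the subject folder during the study, and the electronic data are open to the research team.

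**5. What would the effect be on a mean level?** Let *p* be the share of associates and *d* their mean over-rating in points on the 1-10 scale. Then

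shift in mean = *p* × *d*.

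Neither value is in the documents. With assumed values:

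| *p* | *d* = 0.5 | *d* = 1.0 | *d* = 1.5 |
|---|---|---|---|
| 10% | 0.05 | 0.10 | 0.15 |
| 30% | 0.15 | 0.30 | 0.45 |
| 50% | 0.25 | 0.50 | 0.75 |

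Neither *n* nor the number of surveys per person enters the formula. For a given *p* and *d*, more data do not reduce the shift. For dryness, the bias would mean under-reported symptoms; the direction of the VAS is not stated.

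**6. What would the effect be on change over the day?** If associates over-rate by *d*₁₀ at 10 hours and *d*₁₆ at 16 hours, the mean within-person change, among subjects who answer both surveys, shifts by

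*p* × (*d*₁₆ − *d*₁₀).

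With a constant over-rating, *d*₁₆ = *d*₁₀ and the shift is 0. The documents give no reason to expect associates to decline differently over the day.

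**The case against.** The strongest reply has four parts.

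- **The question is about the course of the day.** The Background section asks how the lens performs into the evening, in the same people at 10, 12, 14 and 16 hours. A constant favourable shift cancels in that comparison. This stands, and it limits the point to levels. The VAS endpoint, however, is planned as end-of-study scales, and the key endpoints name no change score.
- **The surveys are at arm's length.** Evening ratings are completed through a REDCap link. In the morning "the subject will report their time of lens insertion to study staff or by entering the time in a RedCap survey", so even that contact need not be personal. This also stands: it lessens face-to-face pressure. It does not remove the point, because the ratings are not hidden from the team and the final surveys are part of a visit.
- **The size is assumed.** Word of mouth is one route of many, and the text says only that it may occur. OSU employees are also a wider group than the team's own colleagues. This stands. No share of associates can be called likely from these documents.
- **The study is exploratory and descriptive.** No test is planned. Expectation bias from an unmasked single-lens design affects every subject and would remain if friends were excluded. This is true, but it does not justify leaving an avoidable additional source unrecorded when the reported levels are descriptive results.

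A reader might also infer more than the documents support: that the recruitment route is definitely not recorded, that associates will complete more surveys, or that the ratings are the study's only result. The documents are silent on recording and reproduce no case report form. They say nothing on completion by associates. Acuity, lens fit and ocular health are also assessed, though not as key endpoints.

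**Conclusion.** The concern holds as a risk to the reported levels of the key endpoints. The plan opens recruitment to people close to the team, does not exclude them, and does not provide for identifying them. In an open-label, single-lens study with self-rated endpoints, courtesy bias could raise comfort and vision and lower reported dryness.

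The documents do not show that this bias occurs, and its size cannot be derived from them. The range of 0.05 to 0.75 point rests wholly on an assumed share of associates (10% to 50%) and an assumed over-rating (0.5 to 1.5 points). It shows scale and is not an estimate. Within-person change from 10 to 16 hours is unaffected if the over-rating is constant over the evening. The plan is usable without the change, but a reader could not then judge how far the levels depend on associates.

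**What to change.** 1. In the Recruitment section, delete friends from the team-referral sentence.
2. Add an exclusion criterion for study team members, their household members and their close personal contacts. Excluding all staff and students of the College of Optometry is not recommended: it would cut into the planned emails to OSU students, faculty and staff in a study that expects difficult enrolment.
3. Add one item to the Visit 1 form: recruitment route and any relationship to a team member. This is still needed after step 2, because OSU employees known to the team remain eligible and closeness rests on what people declare. It should be collected at entry because it may not be recoverable later.
4. State in the analysis section that, if any associate is enrolled, the evening-rating and VAS summaries will be shown with and without associates. Read these descriptively: in a small sample the comparison may rest on a few people and cannot separate courtesy bias from ordinary differences between persons.

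The cost is a slightly smaller recruitment pool, one data field and one table. Telling subjects that staff do not read individual ratings should not be added, because the Data Management and Security section gives the research team access to the collected data and the assurance could be untrue.

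### Does the one exclusion criterion, worded as a requirement for entry, leave eligibility unclear?

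*Combined protocol and SAP*

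**What the plan says.** The eligibility section of the combined protocol and SAP has ten bullets under Inclusion criteria and one under the heading "Exclusion criteria". That one bullet reads "No current ocular inflammation or infection as assessed by the study investigator".

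Three other places bear on its meaning:

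- **Study Time Points, Visit 1.** An evaluation of "ocular health will occur to determine eligibility", alongside visual acuity and a question about long days of lens wear. The text does not name a disqualifying finding.
- **Inclusion criteria, general health bullet.** Good general health is defined by "medication use that has not changed within the last month" and by the "absence of medical conditions or treatments that are deemed confounding to the data as determined by the PI".
- **Study Time Points, Final visit.** "Subjects will have visual acuity, an assessment of ocular health". This is the next listed ocular health check, because the Visit 2 procedures are given as "Visual acuity and contact lenses fit assessment and over-refraction will be completed".

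**The concern.** An exclusion list names what keeps a person out. This item names the absence of a condition, which is the form of an inclusion requirement. Taken word for word, heading and item together reverse the evident rule: a healthy eye would disqualify and an infected one would not.

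The document does not correct this elsewhere. Inflammation and infection are each mentioned only once, in this bullet, and none of the ten inclusion bullets refers to them. The general health bullet also demands an absence, but it sits under Inclusion criteria, so the protocol's own usage makes the ocular item look misplaced.

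If someone acted on the literal text, the wrong people would be enrolled in a study with survey prompts at up to 16 hours of lens wear. A yes/no eligibility form copied from the list could carry the same reversal.

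**Working it through.** The plan states no figure on this point, so the check is mainly a comparison of texts.

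**1. Is the mismatch real?** Yes. The list has one item, and its wording runs against its heading (1 of 1). Nothing suggests redaction or damage in extraction, since heading and bullet are both intact.

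**2. Which readings are possible?** The bullet has no verb. Reading A: a person with no inflammation or infection is excluded. Reading B: no current inflammation or infection is permitted.

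**3. Which reading fits the rest of the document?**

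| Text | Reading A | Reading B |
|---|---|---|
| Visit 1: ocular health decides eligibility | Only diseased eyes qualify | Diseased eyes are screened out |
| Inclusion: good general health, no confounding conditions | Conflicts in spirit | Fits |
| Inclusion: current lens wearers with good acuity in their own lenses | Hard to combine | Fits |
| Purpose: lens performance on long days of wear | Makes little sense | Fits |

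Reading A fits no row. The item also leaves the judgement to the study investigator, who examines the eye before lenses are dispensed. Reading A would be noticed at once, assuming most candidates have healthy eyes, because it would turn most of them away.

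**4. Is this the only written safeguard?** It is the only item that names ocular inflammation or infection. It is not the only standard available at Visit 1, because the general health bullet lets the PI reject any condition judged confounding, and that can include an eye condition.

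**5. Does the visit schedule add weight?** It could be argued that the wording matters more because ocular health is listed at only 2 of the 3 scheduled visits and the survey days fall between them. The intervals in Study Time Points are:

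- Visit 1 to Visit 2: 7 ± 3 days, so 4 to 10.
- Visit 2 to Final visit: 7 ± 3 days, so 4 to 10.
- Sum: 14 days nominal, 4 + 4 = 8 to 10 + 10 = 20.

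The 8-day minimum cannot hold the five survey days. A 4-day second interval leaves 4 − 1 = 3 days strictly between the visits, or 4 if the evening of Visit 2 is counted. Five survey days need a second interval of at least 5 days (counting that evening) or 6 days (strictly between), so the minimum total is 4 + 5 = 9 or 4 + 6 = 10 days.

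The Study Overview puts the first interval at 1 to 2 weeks, or 7 to 14 days. On that basis the total runs from 7 + 5 = 12 or 7 + 6 = 13 days up to 14 + 10 = 24 days.

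None of these figures depends on the bullet. Rewording it would leave the time between eye examinations exactly as it is, so the intervals do not measure what the wording costs.

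**6. Does any result depend on it?** No. The statistical section plans descriptive statistics on a convenience sample. No endpoint, analysis set or sample size refers to this criterion.

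**The case for a change.** The strongest case for a change is that eligibility text should not need its reader to override the heading. This is the only sentence naming an ocular condition, and correcting it would cost one deleted word or one moved line. It defines part of the only ocular health check listed before participants are asked to report on long days of wear. A protocol is also a source for other documents, and a screening form built from the list could reproduce the reversal.

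Part of this stands. Heading and item do disagree, no other passage states the rule, and the repair would be cheap. But a cheap repair with no effect is still no gain. The point about forms concerns a document that is not in the file, and nothing shows that such a form exists or repeats the wording. The point about the single early eye check concerns the schedule, which the wording does not alter. The argument identifies no reader likely to be misled and no participant likely to be enrolled in error.

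**Conclusion.** The mismatch is real but clerical, and no change to the plan follows. Its extent is one item in a list of one. Its expected effect on enrolment is negligible, and its effect on visits, endpoints, sample size and analysis is nil.

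This rests on two assumptions: that the investigator assessing ocular health at Visit 1 applies the evident sense of the item, and that any screening form follows that sense too. The first is well supported by the Visit 1 text and the general health criterion. The second cannot be checked from the document, but nothing in it points the other way.

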Subjects who, after study team member coaching, are not able to provide analyzable data may be dismissed from the study. Analyzable data is, for example, that which is obtained for the entire measurement interval and provides a readable eye image. Data may not be analyzable if patient isn't able to stand or move freely to utilize the equipment, to name just two causes issues. These issues are usually revealed at the screening assessment visit. Subjects who cannot provide analyzable data will be dismissed for the study. Subjects who do not keep scheduled visits within the required time frame will be dismissed from the study. Study team members will make reasonable efforts to accommodate subjects' schedules.

Protocol Violations, Discontinuation

In the event that a member of the study team or a representative of sponsor becomes aware of a major protocol violation, the IRB shall be notified within 10 working days.

References

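### Does a dismissal rule built around an eye image and equipment that no visit describes put the survey results at risk?

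*Combined protocol and SAP*

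**What the plan says.** The Subject Dismissal section has two parts. One concerns visits missed or outside their window and is not at issue here. The other concerns data quality. Subjects who, after coaching, "are not able to provide analyzable data may be dismissed from the study". Adequate data are then illustrated: "Analyzable data is, for example, that which is obtained for the entire measurement interval and provides a readable eye image". One cause of failure is a subject not being "able to stand or move freely to utilize the equipment". The section adds: "These issues are usually revealed at the screening assessment visit". It then closes the point in firmer terms: "Subjects who cannot provide analyzable data will be dismissed for the study".

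The data the study plans to collect are of another kind. Under Study Time Points, staff collect evening ratings by "sending a link to complete a brief survey at 10, 12, 14 and 16 hours of lens wear that day", and "The surveys will be deployed on 5 days between Visit 2 and Visit 3". For the final visit the plan is: "Subjects will have visual acuity, an assessment of ocular health. Subjects will then complete surveys about their lens wear experience". Key Endpoints lists subjective comfort and vision during extended wear, and a visual analogue scale (VAS) survey of symptoms. The statistical section plans descriptive statistics only, on a small sample chosen for convenience.

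**The concern.** Three things look wrong. First, the example of adequate data needs an image and a measurement interval, and the procedures describe neither. Second, no criterion is given for the data that matter, such as how many evening surveys or survey days are enough. Third, the same subjects may be dismissed according to one sentence and will be according to another.

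The worry with most statistical content concerns the phrase about the entire measurement interval. If staff took that interval to be the 10 to 16 hour survey period, a subject who removed lenses before 16 hours could be judged not to have supplied adequate data. Staying in the study would then depend on late-day wear, which is what the study sets out to describe, and the remaining subjects would be those who tolerate long wear best. A subject dismissed before the final visit would also lack the end-of-study VAS scores, which are a key endpoint.

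**Working it through.** The question is mainly textual, and the documents give no sample size, response rate or early-removal rate from which to estimate an effect.

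**Step 1: does the wording match the procedures?** The procedures under Study Time Points are:

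| Occasion | Planned procedures | Eye image or named equipment |
|---|---|---|
| Visit 1 | Acuity, ocular health, lens fit, over-refraction, initial survey | None described |
| Visit 2 | Acuity, lens fit, over-refraction | None described |
| Five survey days | Insertion time, brief REDCap surveys | None described |
| Final visit | Acuity, ocular health, surveys | None described |

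That is 0 of 3 visits and 0 of 5 survey days. The mismatch is real. Ocular health checks may well use clinic instruments, but none is named.

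**Step 2: do the two dismissal sentences conflict?** One could take the permissive sentence as covering the coaching stage and the mandatory one as the end result. But the permissive sentence already applies after coaching, so both cover the same subjects. The conflict is real too.

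**Step 3: does the rule reach the evening surveys?** Four features of the text point away from that.

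- The image and interval are introduced as an example, so the image is not a condition every subject must meet.
- The rule is about subjects who are unable to give usable data despite coaching. A missed survey link or an early lens removal is not an inability of that kind, and no section makes either a ground for dismissal.
- Problems are expected to appear at screening. No visit carries that name, but eligibility is settled at Visit 1, before any evening survey is sent.
- Elsewhere the protocol attaches measurement to visits: Data Management and Security speaks of a last measurement visit, and the consent section pairs screening with measurement.

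**Step 4: what would one dismissal cost?** Five survey days at four times give 5 × 4 = 20 evening surveys per subject. Dismissal after survey day d leaves 4 × (5 − d) uncollected: 16 of 20 for d = 1 and 8 of 20 for d = 3. Dismissal before the final visit also loses the 2 × 3 = 6 VAS scales (overall and end of day, for vision, comfort and dryness) and the CLDEQ8. The Study Overview instead speaks of surveys each night for one week, which on a seven-night reading would be 7 × 4 = 28. Five days is better supported, because both Study Time Points and the inclusion criteria state it.

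These counts hold for a dismissal for any reason. They do not measure the effect of this wording, because they say nothing about how often it would be applied.

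**The case for a change.** The strongest case for a change is that a rule which may be mandatory should not be left for staff to interpret. Calling the image an example does not supply a criterion for survey data, and none appears elsewhere. Eligibility rests on a yes or no question about long days of wear, with no minimum number of hours, so some enrolled subjects may well stop wear before 16 hours. In a small sample each lost subject counts, and nothing says whether partial data enter the tables. The edit would be cheap.

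Much of this is true as description. The wording does not fit, the two sentences disagree, and adequacy of survey data is undefined. What does not stand is the step from there to selective loss of subjects. It needs staff to apply an instrument-recording rule to text-message surveys, against the section's own cues. It is more plausible that nobody is dismissed for lacking an image that is never taken.

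The edit is also less cheap than it seems if it goes further and makes lens-wear status at each hour part of the definition. The evening survey is described as comfort and vision ratings with digital device use, and no item on current lens wear is mentioned, so a new survey question might be needed.

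**Conclusion.** The observation is correct as a point of drafting, but it does not call for a change to the plan. The Subject Dismissal section appears to contain text carried over from an imaging or dry-eye study; the consent section's reference to people with dry eyes fits that reading, though the documents do not say so. Followed as written, it most likely has no effect on who is retained or on what is reported.

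The size of any effect cannot be estimated and may be zero. No hypothesis test, group comparison or power figure depends on the rule. Data Management and Security keeps the questionnaires and data forms of a disenrolled subject, so ratings already given would not be lost. An analyst producing descriptive statistics would ordinarily summarise the surveys received at 10, 12, 14 and 16 hours and show how many subjects responded at each, which fills the gap without a rule in the protocol.

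This rests on two assumptions: that staff do not read the measurement interval as the evening survey hours, and that available ratings are summarised whether or not a subject answers every survey. If subjects were in fact dismissed for missed late surveys or early lens removal, the concern about selective retention would become a live one.
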